## **6. INVESTIGATIONAL MEDICINAL PRODUCT AND COMPARATOR**

### **6.1 STUDY DRUG**

#### **6.1.1 Study Drug Identification**

5% Human Albumin Solution.

#### **6.1.2 Study Drug Manufacturer**

Not applicable. Any preparation of 5% Human Albumin Solution which has marketing authorisation in the UK to be used for this indication and is stocked by local hospital pharmacies at the participating sites, may be prescribed in this study.

#### **6.1.3 Marketing Authorisation Holder**

An example of a Human Albumin Solution MA Holder is Octapharma Limited and the MA number is PL 10673/0030. This is being listed for representative purposes only.

#### **6.1.4 Labelling and Packaging**

No specific arrangements are planned for labelling since we will use the licensed medicinal products that are currently available in the UK.

#### **6.1.5 Storage**

The 5% HAS will be supplied by the local hospital pharmacy department at each participating site. The interventions will be kept in a secure place at each hospital pharmacy under conditions specified in the local internal procedures.

#### **6.1.6 Destruction of Trial Drug**

Not applicable as using hospital routine supplies.

### **6.1.7 Summary of Product Characteristics (SPC) Booklet or Investigators Brochure**

The NHS does not have a preferred brand or generic HAS. Each hospital pharmacy may stock several brands and these may change over the course of the study. The pharmacy can dispense any brand of HAS currently in stock. A representative Summary of Product Characteristics (SPC) (is provided in a separate document with a cover sheet and signature page (signed and verified by the CI and Sponsor) and is filed in the TMF.

## **6.2 COMPARATOR DRUG**

### **6.2.1 Study Drug Identification**

Intravenous “balanced” crystalloid.

### **6.2.2 Study Drug Manufacturer**

Not applicable. Any preparation of intravenous “balanced” crystalloid which has marketing authorisation in the UK to be used for this indication and is stocked by local hospital pharmacies at the participating sites, may be prescribed in this study.

### **6.2.3 Marketing Authorisation Holder**

An example of an Intravenous “balanced” crystalloid MA Holder is Baxter Healthcare Ltd and the MA number is PL 00116/0332. This is being listed for representative purposes only.

### **6.2.4 Labelling and Packaging**

No specific arrangements are planned for labelling since we will use the licensed medicinal products that are currently available in the UK.

### **6.2.5 Storage**

The balanced crystalloid will be supplied by the local hospital pharmacy department at each participating site. It will be kept in a secure place at each hospital pharmacy under conditions specified in the local internal procedures.

### **6.2.6 Destruction of Trial Drug**

Not applicable as using hospital routine supplies.

### **6.2.7 Summary of Product Characteristics (SPC) Booklet or Investigators Brochure**

The NHS does not have a preferred brand or generic intravenous “balanced” crystalloid. Each hospital pharmacy may stock several brands and these may change over the course of the study. The pharmacy can dispense any brand of intravenous “balanced” crystalloid currently in stock. A representative Summary of Product Characteristics (SPC) is provided in a separate document with a cover sheet and signature page (signed and verified by the CI and Sponsor) and is filed in the TMF

### **6.3 DOSING REGIME**

Participants allocated to the treatment arm will receive intravenous 5% Human Albumin Solution (HAS) administered as the sole intravenous resuscitation fluid during the initial 6-hour resuscitation period. It is anticipated that most participants will receive approximately 10ml/kg in the first 3 hours using 250-500ml rapid infusion (bolus) of HAS for resuscitation based on clinical judgement, using clinical assessment supplemented by technology within the usual scope of practice. After 3 hours, further HAS boluses for resuscitation up to 6 hours post-randomisation will be at clinical discretion and will be documented in the eCRF. Both vital signs and lactate, if measured, prior to treatment starting and at 1,3,5,7 hours (+/-30mins) after randomisation, will be recorded in the eCRF as well as source data worksheets or medical notes.

To avoid contamination, participants in the HAS arm should not receive balanced crystalloid or other fluid as a resuscitation fluid in the first 6 hours post randomisation. If the treating clinician believes resuscitation to euvolaemia has been completed within the 6hour period post randomisation and wishes to commence slow maintenance fluid within this timeframe using balanced crystalloid, this should be at a rate of no more than 125ml/hour. The reason for the fluid should be clearly recorded in the eCRF i.e., maintenance rather than resuscitation. In the subsequent event of further clinical deterioration during the intervention timeframe requiring resuscitation fluid, further boluses of HAS should be administered and documented as further bolus fluid for resuscitation.

Participants allocated to the usual care arm will receive intravenous balanced crystalloid administered as the sole intravenous fluid during the initial 6 hour resuscitation period post randomisation. It is anticipated that most participants will receive approximately 30ml/kg in the first 3 hours using 250-1000ml rapid infusion (bolus) of balanced crystalloid for fluid resuscitation based on clinical judgement, using clinical assessment supplemented by technology within the usual scope of practice. Thereafter, further crystalloid boluses for resuscitation up to 6 hours will be at the discretion of the clinical team and will be documented in the eCRF. Both vital signs and lactate, if measured, prior to treatment starting and at 1,3,5,7 hours (+/-30mins), will be recorded in the eCRF as well as source data or medical notes.

Participants in the balanced crystalloid arm should not receive HAS or any other fluid as a resuscitation fluid in the first 6 hours. If the treating clinician wishes to administer maintenance rather than resuscitation fluid this should only be done after resuscitation is complete and should be at a rate of no more than 125ml/hour. The reason for the fluid should be clearly recorded in the eCRF i.e., maintenance rather than resuscitation. In the subsequent event of further clinical deterioration during the intervention timeframe requiring resuscitation fluid, further boluses of balanced crystalloid should be administered and documented as further bolus fluid for resuscitation.

For any participants requiring operative intervention during the 6 hours post randomisation treatment allocation should be maintained where possible in theatre and in critical care after but allow for anaesthetic discretion/judgement around other fluid and blood product use.

### **6.3.1 Difference between current/planned care pathways**

There will be no difference between treatment arms other than intravenous resuscitation fluid in the first 6 hours of care after recruitment. Other care will follow national sepsis guidelines.

## **6.4 PARTICIPANT ADHERENCE**

Adherence with fluid prescription will be a feasibility outcome and will be recorded as part of the eCRF. This does not need to be reported to the Sponsor as a deviation/violation.

## **6.5 CROSSOVER OF TREATMENT ARMS**

If a participant receives the intervention from the arm they were not allocated to within 24 hours of randomisation then this will be recorded as an outcome in the eCRF at discharge. This does not need to be reported to the Sponsor as a deviation/violation.

## **6.6 OVERDOSE**

There are no specific overdose features expected, beyond those associated with excessive intravenous fluid administration. Excess fluid administration will be handled in line with standard practice.

## **6.7 OTHER MEDICATIONS**

### **6.7.1 Non-Investigational Medicinal Products**

There are no NIMPs for this study.

### **6.7.2 Permitted Medications**

Not applicable.

### **6.7.3 Prohibited Medications**

Not applicable.

### **6.7.4 Concomitant Medications**

No concomitant medications will be recorded as part of the eCRF. These will be documented in the medical records and will only be recorded where they are relevant to AE/SAE reporting.

## 7. STUDY ASSESSMENTS

### 7.1 STUDY ASSESSMENTS

The following study assessments will be completed:

	Screening	Baseline (Day 0)	Day 1-6	Day 7	Discharge	Day 30 #	Day 90 #	Day 180
Consent	X							
Eligibility	X							
Randomisation		X						
Demographics/Medical History/estimated weight		X						
Routine blood results*		X	X	X				
Routine urine and other culture results		X						
Vital Signs/lactate**		X						
IMP administration/adherence		X						
Interventions		X						
Mortality					X	X	X	
Length of stay/ Ward/HDU/ICU stay					X		X	
Readmissions							X	
Acute kidney injury/ Pulmonary oedema/ Allergy/anaphylaxis					X			
Adverse Events		X	X	X				
EQ-5D-5L***		X		X				X

\* Daily (+/- 12 hours) for any routine bloods collected up to 7 days. If bloods (or individual parameters) are not requested by the clinical team, this will not be recorded as a deviation.

\*\*Both vital signs and lactate, if measured, will be recorded prior to treatment starting and at 1,3,5 and 7 hours after randomisation (+/-30mins). Lactates up to 24hours post-randomisation, if measured, will be recorded at 9,11,13,15,17,19,21,23 hours (+/-30mins).

\*\*\*First 50 participants only.

# As Day 30 and Day 90 follow up is collected from the medical records it can be reviewed and recorded in the eCRF up to 7 days after the time point so it captures all admissions/events up to and including Day 30 and 90.

For the first 50 participants enrolled in the study, HRQoL will be measured using the EQ-5D-5L at baseline, 7 days and at 180 days. If questionnaires are not completed on the specified day or are not returned by the participant, this will not be reported as a deviation. Vital status will be checked either using local electronic medical records or contact with participant GP prior to contacting participant. Outcome measures will be obtained via the medical notes.

## 7.2 LONG TERM FOLLOW UP ASSESSMENTS

There is no long term follow up for this study – most participants will be followed up for 90 days only, with the first 50 participants being followed up for 180 days.

## 8. DATA COLLECTION

Data will be collected from consent until final follow up visit. Site-specific source data plans will be created to indicate where protocol required information will be originally documented. Source data worksheets created by the Edinburgh Clinical Trials Unit (ECTU) will be made available, but their use is optional. The eCRF can be used as source data for some data points (this should be noted on the source data plan by the site).

Study data will be entered onto an eCRF (case report form) developed by ECTU.

### 8.1 CASE REPORT FORMS

Patients will have data collected during index hospitalisation, comprising of age, sex at birth, past medical history. Data will be collected from NHS records and will include: eligibility criteria, consent and baseline demographics; estimated weight, co-morbidities; vital signs, routine blood results including baseline kidney function, liver function and albumin; relevant investigations or interventions including surgery, vasopressor use, renal replacement therapy, invasive ventilation, chest x-rays, prescriptions; time of start of IMP; length of stay including critical care, repeat hospitalisations, adverse events and decisions regarding treatment escalation planning and resuscitation. Detail will also be collected on the trial intervention including timing and volume of fluids. Length of stay and repeat hospitalisation will be recorded as part of follow up.

Study Data Collected on eCRF
Primary Outcome
30-day mortality
Recruitment rate from screening logs
Secondary Outcomes
In-hospital mortality and 90-day mortality
Time to start of IMP
Data completeness
Study withdrawal
Volume of randomised fluid delivered in each arm in the first 6hrs and 24hrs
Proportion of participants needing critical care intervention: Intravenous vasopressors, renal replacement therapy and invasive ventilation
Proportion of patients who receive any other fluid apart from intervention or control in first 6 hrs after recruitment
Proportion of patients admitted to critical care (HDU/ICU); length of stay in critical care (HDU/ICU)
Length of hospital stay
Proportion of patients readmitted in first 90 days after discharge

Proportion of patients developing any of: acute kidney injury (Defined by NICE ( https://cks.nice.org.uk/acute-kidney-injury#!scenario ); pulmonary oedema (Radiology diagnosis or requirement for rescue management (new diuretic use); and allergy or anaphylaxis (Requirement for rescue management (antihistamines, adrenaline, intravenous fluids, steroids)).
Health Related Quality of life (EQ-5D-5L) at 7 and 180 days for the first 50 patients.
Secondary care costs at 30 days (calculated from readmissions and length of stay at ward level and in critical care (HDU/ICU)

## 8.2 TRIAL DATABASE

Data collected about the participants will be entered into a specially designed password protected online accessed secure database (REDCAP; <http://www.project-redcap.org>) the server of which is held within the University of Edinburgh. Data can be entered directly to the database using is as an eCRF if the research team prefer. Following data analysis, the database will be archived by programmers in ECTU. This archived eCRF/database will be stored indefinitely on University of Edinburgh servers once user access has been disabled. Access to the archived database will be controlled by the Chief Investigator.

## 9. DATA MANAGEMENT

This trial will be coordinated from ECTU. Data will be collected at each site by local investigators and uploaded to the eCRF/database. If a participant or their representative withdraws a previously given informed consent or refuses to consent for continuation in the trial, or if the participant dies and no participant consent is available, the patient's data will be handled as follows: Data collected up to the point of withdrawal will be used in an intention to treat analysis. All data on adverse events, including those routinely collected as outcomes, will be collected and reported as required by the relevant authorities. Where no consent is given by any legal representative, i.e. deferred consent is used and no subsequent consent obtained, or a participant dies before any consent obtained, the patient data collected would be destroyed.

[figure not shown]

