### **5.2.3. Deferred Consent**

Patients who have “life threatening features” and who lack temporary capacity due to their current illness can be recruited to the trial using deferred consent if there is no Personal/Professional Representative to give consent on their behalf within 30 minutes so that treatment can be commenced within one hour. The decision to defer consent should be made by an ST4 (or above) or consultant who has appropriate trial training and this should be clearly documented.

The patient would be enrolled into the trial and receive their allocated treatment. Consent would be sought as soon as possible from a Personal Representative (or a Professional Representative if they are available sooner). If a Personal/Professional Representative declines to give consent for continuation at this stage, their wishes will be respected and the withdrawal process in section 5.6 will be followed.

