### **5.2.4. When the participant regains capacity**

If and when the participant regains capacity to consent (as assessed by a clinician), they will be given a Recovered Capacity PIS which will explain what has happened to them so far and seek written consent for continued participation in the trial. This will be done as soon as it is feasibly possible. If the participant is happy to continue they will be asked to provide written consent. The Investigator or delegated member of the trial team and the participant will sign and date the Consent Form to confirm that consent has been obtained. The original consent form will be filed in the Investigator Site File (ISF), the participant will receive a copy of this document and a copy filed in the participant’s medical notes.

In the event that a patient is not able to be approached for consent to remain in the trial prior to hospital discharge, the local research team will seek written consent by sending a PIS and consent form by post. The patient will be asked to return the signed consent form if they wish to remain in the trial, or contact the study team if they wish to be withdrawn. If there is no response, one further reminder can be send after one month by post. If the patient does not return the signed consent form but

does not ask to be withdrawn from the trial, the Professional Representative and/or Personal Representative consent will remain valid and the patient will remain in the trial.

If the participant is not happy to continue, the withdrawal process in section 5.6 will be followed.

[figure not shown]
For any patient who was included but does not regain full capacity, consent from the Personal Representative will stand, or from the Professional Representative where there is no Personal Representative. Where no consent is given by any legal representative, i.e. deferred consent is used and no subsequent consent obtained, or a participant dies before any consent obtained the patient data collected would be destroyed.

Patients with permanent incapacity will not be recruited and this is an exclusion criteria.

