## **5.6 WITHDRAWAL OF STUDY PARTICIPANTS**

Participants are free to withdraw from the study at any point or a participant can be withdrawn by the Investigator or their Personal/Professional Representative. If withdrawal occurs, the primary reason for withdrawal will be documented in the participant's eCRF, if possible. The participant/their Representative will have the option of withdrawal from:

1. Study treatment with continuation of the collection of clinical and safety data;
2. All aspects of the trial but continued use of data collected up to that point. To safeguard rights, the minimum personal information possible will be collected.

Randomised patients who wish to be withdrawn from the study before they have undertaken any study related procedures will be withdrawn from the study and another participant will be recruited to replace them. Data on the original participant will be kept on the eCRF/database.

We anticipate ~1% withdrawal as previously found in the 3CPO, RATPAC and RAPID-CTCA trials [38-40].

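### Participants whose data are destroyed because consent was never obtained remain in the ITT set as defined, and the analysis sets no bounds on a loss that is partly triggered by death

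*Protocol*

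**What the plan says.** **Entry.** Protocol section 5.2.3 allows deferred consent for patients with life-threatening features who temporarily lack capacity, when neither a personal nor a professional representative can be found within 30 minutes. For these patients, "The patient would be enrolled into the trial and receive their allocated treatment". Consent is sought afterwards.

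**Destruction.** Section 5.2.4 says that where no legal representative has consented, because consent was deferred and never followed up by a consent, "or a participant dies before any consent obtained the patient data collected would be destroyed". Section 9 repeats the rule: "or a participant dies before any consent obtained, the patient data collected would be destroyed".

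**Retention.** Section 9 also covers a participant or representative who withdraws or "refuses to consent for continuation in the trial, or if the participant dies and no participant consent is available". For these cases, "Data collected up to the point of withdrawal will be used in an intention to treat analysis".

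**Analysis set.** SAP section 3 puts every randomised patient in the ITT population, except those who withdrew permission for their data to be held. Protocol section 5.5.1 has the same single exception. SAP section 3 then removes records with a missing outcome from the analysis of that outcome (complete case).

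**Reporting.** SAP 4.1 counts those randomised, those allocated to each arm, withdrawals of consent, reasons for stopping early, and the number in the ITT analysis of the main clinical outcome by arm. SAP 4.6(d) reports missing-data patterns by randomised group.

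**The concern.** Two rules do not meet. The protocol destroys some randomised patients' data because consent was never obtained. The ITT definition removes patients only for an act of withdrawal. A patient nobody could consent for, or who died first, has performed no such act. By definition that patient is analysed, and in practice there is nothing to analyse.

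This is slightly more than wording because of the death branch. There the record is lost because the participant died, and 30-day mortality is the clinical primary outcome. A complete-case rule is not neutral when the outcome itself causes the loss. Each destroyed death lowers that arm's observed mortality, and each destroyed survivor raises it. The trial is open label and consent is sought after allocated treatment has started, so equal loss in the two arms cannot simply be assumed.

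What is at stake is the use in protocol section 10.2: the confidence intervals for the mortality difference and for standard-care mortality are to inform the definitive trial. Those intervals carry no allowance for this loss.

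**Working it through.** **Step 1: the definitions side by side.**

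| Participant under deferred consent | Protocol 5.2.4 and 9 | In ITT set by SAP 3 and protocol 5.5.1? | Record available? |
|---|---|---|---|
| Representative consents later | Kept | Yes | Yes |
| Representative actively refuses | Withdrawal process (5.2.3, 5.6); data to that point kept | Yes, unless storage permission is withdrawn | Yes, to that point |
| No consent ever obtained | Destroyed | Yes (nothing withdrawn) | No |
| Dies before any consent | Destroyed | Yes (nothing withdrawn) | No |

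The mismatch lies in the last two rows. Only the last is triggered by the outcome.

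**Step 2: inputs for size.** 300 participants allocated 1:1 (protocol 4.1, 5.5.1), so I assume 150 per arm. Mortality is 20% (protocol 1.1, index hospitalisation) or 35% (protocol 10.1, 30-day). The number destroyed is not given, so I use 1, 3 and 5 as assumed values.

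**Step 3: the plan's own figure.** Section 10.1 claims 90% power for 35% against 18%. With 150 per arm and pooled rate 0.265, the null standard error is √(2 × 0.265 × 0.735/150) = 0.0510 and the alternative standard error is √((0.35 × 0.65 + 0.18 × 0.82)/150) = 0.0500. Power = Φ((0.17 − 1.96 × 0.0510)/0.0500) = 0.920, or 0.898 with a continuity correction. The stated figure reproduces, so 150 per arm is a fair base. It does not depend on destroyed records.

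**Step 4: deaths lost in one arm only.** With D deaths among 150 and k of them destroyed, observed mortality is (D − k)/(150 − k), and the crude odds ratio is multiplied by (D − k)/D.

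| | 20% (D = 30) | 35% (D = 52.5) |
|---|---|---|
| k = 1 | 29/149 = 19.5% | 51.5/149 = 34.6% |
| k = 3 | 27/147 = 18.4% | 49.5/147 = 33.7% |
| k = 5 | 25/145 = 17.2% | 47.5/145 = 32.8% |
| Odds ratio factor, k = 3 | 27/30 = 0.90 | 49.5/52.5 = 0.94 |

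If both arms lose the same share of deaths and the same share of survivors, the crude odds ratio is unchanged.

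**Step 5: bounds when vital status is unknown.** Let d records be destroyed in each arm, with observed rate p among the other 150 − d, so that x = p(150 − d) deaths are seen. Arm mortality lies between x/150 and (x + d)/150.

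- d = 3, p = 0.20: x = 29.4, giving 19.6% to 21.6%.
- d = 3, p = 0.35: x = 51.45, giving 34.3% to 36.3%.

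With equal observed rates, suppose all destroyed records died in one arm and all survived in the other. The risk difference then moves by ±d/150, which is 0.7, 2.0 or 3.3 points for d = 1, 3 or 5. At d = 3 the crude odds ratio is bounded by [x/(150 − x)] / [(x + d)/(150 − x − d)] and its inverse: 0.885 to 1.130 at 20%, and 0.916 to 1.092 at 35%.

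**Step 6: against sampling error.** The 95% half-width of the difference is 1.96 × √(2p(1 − p)/150), which is 9.1 points at 20% and 10.8 points at 35%. The worst-case bound ±d/150 reaches that size only at d = 13.6 or 16.2, so about 14 or 16 destroyed records per arm.

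**The case against.** **The numbers may be tiny or zero.** Entry is narrow. A professional representative can be a treating doctor independent of the study or someone the healthcare provider nominates, so finding nobody within 30 minutes may be rare. Consent is then pursued as soon as possible. All analyses are exploratory and tests are informal. This stands, and it is why the point is minor.

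**The loss is already visible.** Allocated and analysed numbers by arm are both in SAP 4.1, and 4.6(d) describes missingness by group. Most of the loss can be found by subtraction. This also stands, but the shortfall would be mixed with withdrawals and other missing outcomes, and no line names destroyed records.

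**Destruction is a consent safeguard.** Agreed. Nothing here asks for the data to be kept.

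**Adverse event and outcome data are still to be collected.** Section 9 says such data will be reported as the authorities require. Whether that reaches people who never consented is arguable, and it is not an analysis provision.

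A reader might also infer that section 9 contradicts itself on death, keeping data in one sentence and destroying it in the next. It does not. The destruction sentence is conditioned on no legal representative having consented, while the retention sentence concerns missing consent from the participant. Section 5.2.4 agrees: "For any patient who was included but does not regain full capacity, consent from the Personal Representative will stand".

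Nor do refusal and consent never obtained truly conflict. A representative who "declines to give consent for continuation at this stage" is sent to section 5.6, where one option is withdrawal from "All aspects of the trial but continued use of data collected up to that point". A refusal is also, literally, a case with no later consent, so a cross-reference to 5.6 in section 9 would help, but that is only a wording note.

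**Conclusion.** The point holds as a minor one. The wording mismatch is certain: the ITT set as written includes patients whose records the protocol destroys. It is also certain that one branch of the destruction rule is triggered by the clinical primary outcome, so complete-case analysis is not neutral for the arm mortality rates or their difference.

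A reader might go further and infer that the trial's mortality comparison is materially biased. The documents do not support that. They give no count of deferred-consent entries or destroyed records, no split by arm, and hence no direction. Under the assumption of 150 per arm, three destroyed records per arm give at most ±2.0 points on the risk difference, against a half-width of about 9 to 11 points. Only some 14 to 16 per arm, roughly a tenth of each arm, would match sampling error. The case for acting is that a bound based on counts suits outcome-triggered loss better than complete case alone, and costs little.

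**What to change.** 1. In the ITT definition (SAP section 3), state that records destroyed because consent was never obtained are excluded. Align the single exception in protocol 5.5.1, and note in section 9 that active refusal follows section 5.6.
2. In SAP 4.1, add a line by arm for randomised participants whose data were destroyed for this reason, separate from withdrawals.
3. If that number is not zero, add to SAP 4.4 a crude sensitivity analysis of 30-day mortality by arm and of the risk difference. For each arm, take observed deaths x, destroyed records d, and n as those with known vital status plus d. Report x/n to (x + d)/n for each arm, and the risk difference at both opposite extremes. It has to be crude because the covariates of the adjusted model are destroyed too.
4. Optionally, and only if the ethics committee permits, keep an anonymous tally of vital status by arm and use it in place of the bounds. The SAP abstract reports 300 already recruited, so this may no longer be possible; the bounds need only counts.

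The cost is a sentence in the ITT definition with matching edits to the protocol, one participant-flow line and one table, plus an ethics query if the tally is wanted. The drawbacks are that the bounds become wide if many records are lost, and that the method relies on allocation counts surviving destruction, which the documents do not confirm.
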